Appendix II Description of criteria for Adverse Events of Special Interest

A two-level approach is pursued to analyze potential immune-related adverse events (AEs):

1. A MedDRA Preferred Term (PT) query is used for each event category (i.e., immune-mediated rash, colitis, pneumonitis, hepatitis, nephritis and renal dysfunction, endocrinopathies and other immune-mediated adverse reactions).
2. AEs identified by the MedDRA PT queries will then be medically reviewed using pre-defined case definitions for immune-mediated adverse reactions.

Level 1:

To identify potentially immune-mediated AEs, MedDRA PT queries will be used to search for AEs of interest in the clinical database. The relevant event categories and corresponding MedDRA PT queries are documented in a version-controlled repository maintained by the Sponsor and finalized for analysis of the current study data prior to DB lock.

The respective MedDRA PT queries will be used to identify AEs reported in the current study that are potentially immune-mediated events.

Level 2:

In a second level (medical review), the potential immune-mediated AEs identified from the search performed at Level 1, will be reviewed by qualified medical personnel to determine whether the AE meets the criteria (case definition) for an immune-mediated adverse reaction based on the following algorithm:

Table 13 Algorithm for immune-related adverse reactions

| Criteria | Description |
|---|--|
| Onset | AE onset after 1st avelumab administration until up to 90 days after last dose |
| Duration | AE does not spontaneously resolve (i.e., without corticosteroids/ immunosuppressant treatment) within 7 days after onset |
| Immunosuppressive therapy | AE treated with corticosteroid or other immunosuppressant therapy. For endocrinopathies only: AE required hormone replacement* and /or (corticosteroid or other immunosuppressive therapy) |
| Etiology | No other clear etiology or Histopathology/biopsy consistent with immune-mediated event |
| All criteria listed in the left column need to be fulfilled for an event to meet the case definition of immune-mediated reaction. | |
| *Hormone replacement will be evaluated for specific endocrinopathy disorders only as follows: 
 • Thyroid disorders (HLT): Thyroid therapy (ATC codes (H03A, H03B)) • Diabetes mellitus (including hyperglycemia): Insulin (ATC code A10A) | |

Infusion related reactions are identified based on a list of MedDRA PTs and criteria on the timely relationship according to Table 14.

Table 14 Criteria for infusion related reactions

| | |
|----------------------------|---|
| Infusion related reactions | 
Reactions - Considered when onset is on the day of avelumab infusion (during or after the infusion) or the day after the avelumab infusion (irrespective of resolution date):
 
• Infusion related reaction• Drug hypersensitivity• Anaphylactic reaction• Hypersensitivity• Type 1 hypersensitivity 
Signs and Symptoms - occurring on the day of avelumab infusion (during or after the infusion) and resolved with end date within 2 days after onset
 
• Pyrexia• Chills• Flushing• Hypotension• Dyspnea• Wheezing• Back pain• Abdominal pain• Urticaria |
|----------------------------|---|

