6.5.4.1 Infusion-Related Reactions

A. Symptoms

- Fever
- Chills
- Rigors
- Diaphoresis
- Headache

B. Management (and according to [Table 4](#))

Table 4 Treatment Modification for Symptoms of Infusion-Related Reactions Caused by Avelumab

NCI-CTCAE Grade	Treatment Modification for Avelumab
Grade 1 – mild Mild transient reaction; infusion interruption not indicated; intervention not indicated.	Decrease the avelumab infusion rate by 50% and monitor closely for any worsening.
Grade 2 – moderate Therapy or infusion interruption indicated but responds promptly to symptomatic treatment (for example, antihistamines, NSAIDs, narcotics, IV fluids); prophylactic medications indicated for ≤ 24 h.	Temporarily discontinue avelumab infusion. Resume infusion at 50% of previous rate once infusion-related reaction has resolved or decreased to at least Grade 1 in severity, and monitor closely for any worsening.
Grade 3 or Grade 4 – severe or life-threatening Grade 3: Prolonged (for example, not rapidly responsive to symptomatic medication and/or brief interruption of infusion); recurrence of symptoms following initial improvement; hospitalization indicated for clinical sequelae. Grade 4: Life-threatening consequences; urgent intervention indicated.	Stop the avelumab infusion immediately and disconnect infusion tubing from the subject. Subjects have to be withdrawn immediately from avelumab treatment and must not receive any further avelumab treatment.

IV=intravenous, NCI-CTCAE=National Cancer Institute-Common Terminology Criteria for Adverse Event, NSAIDs=nonsteroidal anti-inflammatory drugs.

Once the avelumab infusion rate has been decreased by 50% or interrupted due to an infusion-related reaction, it must remain decreased for all subsequent infusions. If a subject experiences a Grade 3 or 4 infusion-related reaction at any time, the subject must discontinue avelumab.

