17.1 Adverse Events

Treatment emergent adverse events (TEAEs) are those events with onset dates occurring during the on-treatment period or if the worsening of an event is during the on-treatment period.

All analyses described in Section 17.1 will be based on TEAEs (started during the on-treatment period) if not otherwise specified. The AE listings will include all AEs (whether treatment-emergent or not). A separate listing including AEs started after the on-treatment period will also be provided.

- **Related Adverse Events:** adverse events with relationship to study treatment (as recorded on the AE eCRF page, Relationship with study treatment = Related) reported by the

investigator and those of unknown relationship (i.e. no answer to the question “Relationship with study treatment”).

- **Serious Adverse Events (SAE):** serious adverse events (as recorded on the AE eCRF page, Serious Adverse Event = Yes).
- **Adverse Events Leading to Treatment Discontinuation:** adverse events leading to permanent discontinuation of study treatment (as recorded on the AE eCRF page, Action taken with study treatment = Drug withdrawn).
- **Adverse Events Leading to Death:** adverse event leading to death (as recorded on the AE eCRF page, Outcome = Fatal, as well as AEs of Grade 5).
- **Infusion Related Reaction:** IRRs (as identified according to a pre-specified search list of MedDRA PTs, documented in a version-controlled repository maintained by the Sponsor and finalized for analysis of the current study data prior to DB lock) with onset on study drug dosing date (not prior to infusion of study drug) or the day following study drug infusion.
- **Immune Related Adverse Events (irAE):** irAEs are identified according to a pre-specified search list of MedDRA PTs, documented in a version-controlled repository maintained by the Sponsor and finalized for analysis prior to DB lock.

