According to the protocol, preplanned dose reductions are not allowed for avelumab; however, interruptions in delivering the planned dose that resulted in an actual non-zero dose < 90% of the planned dose are defined as partial doses within an administration for avelumab. The number and percentage of subjects with at least one partial dose as well as a breakdown of partial doses per subject (1 / 2 / 3 / ≥4) will be summarized. In addition, the number and percentage of subjects with at least one infusion rate reduction of 50% or more will be summarized.

Dose Delays

Delays will be derived based on infusion date and will be grouped into the following categories based on the deviation of the actual to the planned treatment administration day (relative to the previous treatment administration date):

- No delay (including 1-2 days delays)
- 3-6 days delay
- 7-13 days delay
- 14-20 days delay
- 21-27 days delay
- ≥ 28 days delay

For example, if one subject receives the study drug on Day 1, then the next study drug administration date will be on Day 15; however, if the subject receives the study drug at Day 16 or 17, this is considered as ‘no delay’.

Number of subjects with delayed infusions and maximum length of delay, i.e. the worst case of delay if subjects have multiple dose delays will be summarized.

A listing of study drug administration will be created with the information collected on the “Avelumab Administration Details” eCRF page.

16 Endpoint Evaluation

In the interim analysis, the efficacy endpoints analysis will be conducted for each of the following subsets of FAS:

- Subjects in FAS with ≥ 6 weeks duration of follow-up
- Subjects in FAS with ≥ 3 months duration of follow-up
- Subjects in FAS with ≥ 6 months duration of follow-up

The primary endpoint and secondary endpoint analysis on FAS will be repeated for the PP analysis set as a sensitivity analysis if the PP analysis set includes less than 95% of subjects in the FAS. This sensitivity analysis will only be performed for subjects with ≥ 6 months duration of follow-up.

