17.1 Adverse Events

Treatment emergent adverse events (TEAEs) are those events with onset dates occurring during the on-treatment period or if the worsening of an event is during the on-treatment period.

All analyses described in Section 17.1 will be based on TEAEs (started during the on-treatment period) if not otherwise specified. The AE listings will include all AEs (whether treatment emergent or not). A separate listing including AEs started after the on-treatment period will also be provided.

- **Related Adverse Events:** adverse events with relationship to study treatment (as recorded on the AE eCRF page, Relationship with study treatment = Related) reported by the investigator and those of unknown relationship (i.e. no answer to the question “Relationship with study treatment”).
- **Serious Adverse Events (SAE):** serious adverse events (as recorded on the AE eCRF page, Serious Adverse Event = Yes).
- **Adverse Events Leading to Treatment Discontinuation:** adverse events leading to permanent discontinuation of study treatment (as recorded on the AE eCRF page, Action taken with study treatment = Drug withdrawn).
- **Adverse Events Leading to Death:** adverse event leading to death (as recorded on the AE eCRF page, Outcome = Fatal, as well as AEs of Grade 5).

- **Immune Related Adverse Events (irAE):** immune related adverse events according to case definition classified by medical review as specified in Appendix II.
- **Infusion Related Reactions (IRR):** IRRs as specified in Appendix II.

Unless otherwise stated adverse events will be displayed in terms of frequency tables: PT and primary System Organ Class (SOC) by decreasing frequency. If an adverse event is reported for a given subject more than once during treatment, the worst severity and the worst relationship to study treatment will be tabulated. Each subject will be counted only once within each PT or SOC and recording period. If a subject experiences more than one AE within a PT or SOC for the same recording period, only the AE with the strongest relationship or the worst severity, as appropriate, will be included in the summaries of relationship and severity.

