17.2.3 Other Significant Adverse Events

The following tables will be created for treatment emergent irAEs:

- The overall summary of irAEs table will include the following categories:
 - All irAEs
 - irAEs leading to death
 - Related irAEs leading to death
 - irAEs
 - irAEs, Grade ≥ 3
 - Related irAEs
 - Related irAEs, Grade ≥ 3
 - irAEs leading to permanent treatment discontinuation
 - Related irAEs leading to permanent treatment discontinuation

- irAEs by worst grade
- Related irAEs by worst grade
- irAEs leading to death, by subcategory and PT
- Related irAEs leading to death, by subcategory and PT
- irAEs by subcategory and PT
- irAEs, grade ≥ 3 , by subcategory and PT
- Related irAEs by subcategory and PT
- Related irAEs, grade ≥ 3 , by subcategory and PT
- irAEs leading to permanent treatment discontinuation by subcategory and PT
- Related irAEs leading to permanent treatment discontinuation by subcategory and PT
- irAEs by subcategory and PT and worst grade
- Related irAEs by subcategory and PT and worst grade

The listing of irAEs will also be provided with the relevant information. The following information will be provided for each irAE:

- The time from first study treatment to start of AE
- The time from most recent study treatment until start of AE
- The duration of the AE

In addition, a listing of irAEs with onset after the on-treatment period will also be provided.

The frequency (number and percentage) of subjects with each of the following will be presented for treatment emergent IRRs:

- IRRs leading to death, by PT
- Related IRRs leading to death, by PT
- IRRs, by PT
- IRRs, Grade ≥ 3 , by PT
- Related IRRs, by PT
- Related IRRs, Grade ≥ 3 , by PT
- IRRs leading to permanent treatment discontinuation, by PT
- Related IRRs leading to permanent treatment discontinuation, by PT
- Serious IRRs, by PT
- Related serious IRRs, by PT
- Time related to first onset of an IRR (infusion 1, infusion 2, infusion 3, infusion 4 or later)

The listing of all IRRs will also be provided with the relevant information with a flag for IRRs with onset outside of the on-treatment period.

CCI

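### Part B's infusion-reaction list (SAP Table 14) omits headache and diaphoresis, which the protocol names as reaction symptoms, so a reaction recorded only under either term is not counted as an IRR

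*SAP*

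**What the plan says.** Protocol Section 6.5.4.1 opens with five symptoms of an infusion-related reaction: fever, chills, rigors, diaphoresis and headache. Table 4 in the same section then sets out handling by grade. For Grade 1 it reads "Decrease the avelumab infusion rate by 50% and monitor closely for any worsening".

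Section 17.1 of the Part B SAP defines the analysis category only by reference: "IRRs as specified in Appendix II". Appendix II then states that "Infusion related reactions are identified based on a list of MedDRA PTs and criteria on the timely relationship according to Table 14". Table 14 has two groups:

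- Five reaction terms (infusion related reaction, drug hypersensitivity, anaphylactic reaction, hypersensitivity, type 1 hypersensitivity): "Considered when onset is on the day of avelumab infusion (during or after the infusion) or the day after the avelumab infusion", whatever the resolution date.
- Nine sign and symptom terms (pyrexia, chills, flushing, hypotension, dyspnea, wheezing, back pain, abdominal pain, urticaria): "occurring on the day of avelumab infusion (during or after the infusion) and resolved with end date within 2 days after onset".

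This definition feeds the two IRR rows of the overall adverse event summary (17.1.1). It also feeds the IRR tables in 17.2.3, which cover death, grade, relatedness, discontinuation and seriousness, together with "Time related to first onset of an IRR (infusion 1, infusion 2, infusion 3, infusion 4 or later)".

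Separately, Section 15 of the Part B SAP plans an exposure summary: "the number and percentage of subjects with at least one infusion rate reduction of 50% or more will be summarized".

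**The concern.** The protocol (Section 3.6) names infusion-related reactions as one of two primary risks of avelumab, so the Part B IRR tables are where a reader will look for their frequency. The sponsor chose to count reactions recorded only as symptoms, since Table 14 has nine bare symptom terms. Having made that choice, it left out two of the five symptoms that its own protocol names.

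Non-specificity does not explain the gap, because back pain and abdominal pain are on the list. No later step recovers a missed event either: the two-level medical review in Appendix II applies to potential immune-related events, not to infusion reactions. Section 9 of the Part B SAP says the protocol's methods were adopted, and the modification history does not mention the term list. At stake is whether the IRR tables miss reactions of a kind the protocol tells sites to recognise.

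**Working it through.** The plan gives no figure to reproduce. The check compares the two lists term by term and then follows each way of recording a reaction through to the tables.

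**Step 1. Protocol 6.5.4.1 against Part B Table 14**

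| Protocol symptom | Table 14 term | Counts if recorded only as the symptom? |
|---|---|---|
| Fever | Pyrexia | Yes, if on the infusion day and resolved within 2 days |
| Chills | Chills | Yes, same rule |
| Rigors | Not named | Depends on whether it codes to chills; the documents do not say |
| Diaphoresis | None | No |
| Headache | None | No |

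Table 14 has 5 + 9 = 14 terms. Two of the five protocol symptoms, diaphoresis and headache, match none of them.

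**Step 2. How the same reaction fares under different recording**

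- Reported as infusion related reaction, with sweating or headache as features: counted, with onset on the infusion day or the day after.
- Reported as headache together with chills on the infusion day, the chills resolving within 2 days: the subject is counted, through chills.
- Reported only as headache, or only as sweating, on the infusion day: not an IRR under Table 14, however short the event. It stays in the tables of treatment-emergent events by system organ class and preferred term (17.1.1) and in the adverse event listings (17.1).
- Reported only as back pain on the infusion day and resolved within 2 days: counted.

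The third and fourth cases are the inconsistency. A symptom that the protocol does not list counts by itself, and one that it does list does not.

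**Step 3. Size**

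The needed input is the number of subjects whose only record of a reaction is headache or diaphoresis. The documents do not give it. At the planned 112 subjects, each such subject would change the subject-level IRR percentage by 1/112 = 0.9 percentage points. That is a unit of scale, not an estimate of the undercount.

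**The case against.** The strongest reply is that the two lists serve different purposes. Section 6.5.4.1 helps sites recognise and manage a reaction; Table 14 is a pre-specified analysis definition, and nothing requires them to match. A site that changes the infusion under Table 4 has already judged the event to be an infusion-related reaction and may well record it as one, in which case it counts. Nothing drops out of safety reporting, because a headache is still tabulated by term, grade and relatedness. Adding headache to a list with no causality criterion would also bring in unrelated headaches.

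Most of this is fair, and it limits the point to events recorded by symptom alone. It does not remove the point: the nine symptom terms show that the sponsor expects such records, and the SAP does not explain why these two symptoms are treated differently.

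A reader might infer more than the documents support:

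- That every reaction with headache or sweating is lost. It is not; the reaction terms and companion symptoms capture many recording patterns.
- That rigors is also lost. That depends on dictionary coding, which the documents do not show.
- That the rate-reduction summary contradicts the IRR tables. It is an exposure output, is not defined by IRR status, and is not meant to reconcile with them.
- That the symptom window should extend to the day after infusion because Part A's does: "with onset on study drug dosing date (not prior to infusion of study drug) or the day following study drug infusion". A same-day window for non-specific symptoms is a defensible choice for specificity, and Part A's term list is held in a sponsor repository that is not shown, so the two parts cannot be compared on this.

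**Conclusion.** The point holds in a narrow form, for Part B only. Table 14 omits two symptoms that the protocol names, while accepting nine other bare symptom terms. A reaction recorded solely as headache or diaphoresis is therefore left out of the Part B IRR tables, though it remains visible elsewhere in the safety output.

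The size is unknown, and any percentage would be a guess. For these two terms the effect can only be to leave reactions out. It would be tempting to conclude that the reported IRR rate is too low overall, but that does not follow: the nine listed symptom terms need no causal link to avelumab, so they can add unrelated events, and the net direction is not established.

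The conclusion assumes that some reactions are recorded by symptom alone. Table 14's design implies this, but the documents do not count them. The outputs are descriptive and the primary endpoint is unaffected, so this is an inexpensive improvement and not a serious defect.

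**What to change.** Keep the present Table 14 as the main definition if the sponsor prefers it, for example for consistency with other avelumab studies. Then:

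1. Add a supplementary row to the Part B IRR tables that counts the Table 14 terms plus headache and diaphoresis/hyperhidrosis, using the existing sign and symptom timing rule (infusion day, resolved within 2 days).
2. Optionally, restrict the two added terms to events that the investigator judged related, which limits the number of unrelated headaches.
3. Provide a listing of subjects with an infusion rate reduction of 50% or more and no IRR, so that a reader can see whether symptom-only reactions are being missed.
4. State in Appendix II why the main list differs from protocol Section 6.5.4.1.

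The cost is a short SAP edit, some extra table rows and one listing, from adverse event and exposure data already planned for analysis. The supplementary row may show a slightly higher IRR rate and may include a few unrelated events.

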Missing statistics, e.g. when they cannot be calculated, should be presented as 'ND' or 'NA'. For example, if N=1, the measure of variability (SD) cannot be computed and should be presented as 'ND'.

Partial dates will be imputed as follows:

Disease history

Incomplete dates for disease history (initial diagnosis date, date of documented, locally advanced, inoperable or metastatic disease diagnosis, date of response or progression in prior treatment) will be imputed as follows:

- If the day is missing, it will be imputed to the 15th day of the month.
- If both day and month are missing and the year is prior to the year of the first study treatment, the month and day will be imputed as July 1st.
- If both day and month are missing and the year is same as the year of the first study treatment, the month and day will be imputed as January 1st.
- If the date is completely missing, no imputation will be performed.

Adverse events

Incomplete AE-related dates will be imputed as follows:

- If the AE onset date is missing completely, then the onset date will be replaced by the start of study treatment.
- If only the day part of the AE onset date is missing, but the month and year are equal to the start of study treatment, then the AE onset date will be replaced by the start of study treatment. For example, if the AE onset date is --/JAN/2015, and study treatment start date is 15/JAN/2015, then the imputed AE onset date will be 15/JAN/2015.
- If both the day and month of the AE onset date are missing but the onset year is equal to the start of study treatment, then the onset date will be replaced by the start of study treatment. For example, if AE onset date is --/---/2014, and study treatment start date is 19/NOV/2014, then the imputed AE onset date will be 19/NOV/2014.
- In all other cases the missing onset day or missing onset month will be replaced by 1.

- Incomplete stop date will be replaced by the last day of the month (if day is missing only), if not resulting in a date later than the date of subject's death. In the latter case the date of death will be used to impute the incomplete stop date.
- In all other cases the incomplete stop date will not be imputed.

Prior/concomitant medication

Incomplete prior/concomitant medication dates will be imputed as follows:

- If the medication date is missing completely, then the medication date will be replaced by the start of randomized treatment.

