Changes in toxicity grade, seriousness or outcome of AEs are recorded as separate entries in the eCRF with associated end and start dates (start date equals end date of previous entry). Such entries reporting the same event in such immediately consecutive periods will be considered as one event in the analysis in case of an improvement in toxicity grade. These events will be kept as separate records in the database in order to maintain the full detailed history of the events. The start date of the initial record in the sequence is taken as start date of the entire event. Duration of the AE and the TEAE flag will be adjusted accordingly in the analysis.

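### Part B SAP Table 14 counts nine symptom terms as infusion-related reactions only if they resolve within 2 days, so the severe-IRR rows of Section 17.2.3 can miss longer, ongoing or fatal symptom-only events; a labelled upper count for those rows would bound the gap.

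*SAP*

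**What the plan says.** Section 17.1 of the Part B SAP gives no IRR definition of its own; it points to the appendix: "IRRs as specified in Appendix II". Table 14 there has two tiers.

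- **Five reaction terms** (infusion related reaction, drug hypersensitivity, anaphylactic reaction, hypersensitivity, type 1 hypersensitivity). These count if onset is on the infusion day or the day after, "irrespective of resolution date".
- **Nine sign and symptom terms** (pyrexia, chills, flushing, hypotension, dyspnea, wheezing, back pain, abdominal pain, urticaria). These count only with onset during or after the infusion on the infusion day and if "resolved with end date within 2 days after onset".

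No exception is made for severe, serious, ongoing or fatal symptom events. The medical-review level in Appendix II applies to immune-related events, not to IRRs. Section 17.2.3 then tabulates treatment-emergent IRRs overall and by outcome, including "IRRs leading to death, by PT", "Serious IRRs, by PT", Grade ≥ 3 and permanent discontinuation, each with a related-only version.

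Two further rules bear on event length. Section 17.1 joins immediately consecutive records of the same event, which "will be considered as one event in the analysis in case of an improvement in toxicity grade". Section 11 handles adverse event stop dates that lack a day: "Incomplete stop date will be replaced by the last day of the month (if day is missing only"), capped at the date of death. Other incomplete stop dates are not imputed.

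**The concern.** For the nine terms, entry to the severe rows depends on prompt resolution, and those rows then report outcomes (serious, fatal, drug withdrawn) that may go with slow resolution or none. Relative to a definition based on onset alone, the limit can only lower these counts. A symptom-only recording is foreseeable, since Table 14 lists symptom terms for that very purpose.

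Protocol Section 3.6 names infusion-related reactions as one of the two primary risks of avelumab. At stake is whether the Part B severe-IRR rows can be read as complete for infusion-day events, or only as complete for diagnosed reactions plus short-lived symptoms. The Part A SAP (Section 17.1) defines IRRs by a term list and onset timing with no resolution condition, so the two parts of the trial also differ on this point. The Part A term list is not in the documents, so the counts cannot be compared.

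**Working it through.** The plan states no figure for this rule, so there is none to reproduce. The check has three steps.

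**Step 1: run cases through the rule.** Each case has onset during or after infusion on the infusion day (day 1) and is recorded only under one of the nine terms. The test is end date minus onset date ≤ 2 days, and resolved.

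| Case | In the Table 14 severe row? | In a count that ignores end dates? |
|---|---|---|
| Grade 3, ends 1 day after onset | Yes | Yes |
| Grade 3, ends 4 days after onset | No | Yes |
| Serious, ongoing at cut-off | No (no end date) | Yes |
| Drug withdrawn, lasts 3 days | No | Yes |
| Grade 3 on day 1, Grade 1 to day 5 (merged as one event) | No (5 − 1 = 4 > 2) | Yes |
| Fatal on day 2 | No if resolution is required; possibly if only the end date is programmed | Yes |

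The SAP does not say how the fatal case is to be programmed. An event that also carries one of the five reaction terms is counted under that term.

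**Step 2: size per subject.** With 112 planned subjects, one affected subject lowers a row's rate by 1/112 = 0.89 percentage points. How many subjects are affected cannot be derived from the documents.

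**Step 3: stop dates that lack only the day.** Take a symptom that truly ended on its onset day d, in a month whose last day is L. The imputed stop date is L, which adds L − d days.

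- The limit is met only if L − d ≤ 2, that is, onset on one of the last 3 days of the month: 3 × 12 = 36 days in a 365-day year.
- Pass: 36/365 = 9.9%. Fail: 329/365 = 90.1%.
- If the onset day counts as the first of the 2 days, the test is L − d ≤ 1. Then 2 × 12 = 24 days pass (6.6%) and 341/365 = 93.4% fail.
- Mean added length in such a year, summing L(L − 1)/2 over months: (7 × 465 + 4 × 435 + 378)/365 = 5373/365 = 14.7 days.

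These shares assume onsets spread evenly over the calendar and apply only to events whose stop day is missing. The SAP does not say outright that the imputed date feeds the Table 14 test. If it does not, such an event has no complete end date and still cannot be shown to meet the limit.

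**The case against.** The strongest case for the plan is that the limit does useful work. Dyspnea, back pain, abdominal pain and fever have many causes in metastatic disease, and dosing every 2 weeks makes chance overlap with an infusion day likely. Without a duration limit, a persistent tumor symptom that began on an infusion day would count as an IRR. This stands, and it is why Table 14 should remain the main definition.

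Three stronger readings are tempting, and the documents do not support them.

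- **That the limit screens out severe reactions as such.** Protocol Table 4 opens its Grade 3 description with "Prolonged (for example, not rapidly responsive to symptomatic medication and/or brief interruption of infusion"), which invites this. But Table 4 sets no duration for Grade 3; the only duration it gives is 24 hours, for prophylactic medication under Grade 2. A Grade 3 reaction can resolve well within 2 days. Table 4 also requires withdrawal after a Grade 3 or 4 infusion-related reaction, so an investigator acting on it has made the diagnosis and may well report the unrestricted term. Protocol Section 7.4.1.1 asks for the primary cause of death, so a fatal reaction coded only as, say, chills is unlikely.
- **That safety information is lost.** The excluded events remain in the Part B tables of treatment-emergent events by grade and of deaths (17.1.1), discontinuations (17.1.2) and serious events (17.2.2). The death listing in 17.2.1 shows dosing dates.
- **That month-end imputation would remove most short symptom reactions.** The 90% figure is conditional on a missing stop day, and no rate of missing stop days is given. Protocol Section 7.4.1.2 asks for resolution dates, the Part B SAP (Section 8) uses cleaned data, and Section 11 flags imputed values in listings. Such events may be rare.

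What survives is narrower: for the nine terms, the severe rows can only under-count relative to onset timing, and the plan offers nothing that shows by how much.

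**Conclusion.** The point holds as a classification gap in four IRR rows and their related-only versions. In Part B, an infusion-day event recorded only under one of the nine symptom terms is left out of the Grade ≥ 3, serious and discontinuation rows if it lasts more than 2 days or is ongoing. It is left out of the death row if it is fatal, provided that resolved is read in its ordinary sense. The any-IRR row is reasonably defined and needs no change.

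The size is 0.89 percentage points per affected subject, with an unknown number affected that may be zero. The conclusion rests on events being recorded under a symptom term alone. The imputation problem is a minor addition of unknown frequency. No efficacy result is touched. It is worth acting on because the remedy is cheap and the risk is one the protocol singles out.

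**What to change.** Keep Table 14 as the main definition. Add to Part B SAP Section 17.2.3 one prespecified sensitivity count for the Grade ≥ 3, serious, death and discontinuation rows, all and related. It would comprise the Table 14 IRRs plus any event under the nine terms with onset during or after infusion on the infusion day, whatever its end date. Label it an upper count, because some of these events may be tumor-related. Since it ignores end dates, it also recovers events in those rows that fail only through month-end imputation, and it removes the ambiguity over fatal symptoms.

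In the IRR listing, show with a flag any symptom event excluded only because its stop date was imputed. The date test in the main definition should not be rewritten. Testing against the earliest possible stop date, for example, would alter the any-IRR row and pass every event whose stop month is its onset month, even one lasting over three weeks.

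The cost is a short SAP addition and a few lines of code on adverse event data already collected. The drawback is that the upper count may include a few infusion-day symptoms unrelated to the infusion, which its label makes plain.
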